Ethical and Lagal Aspects	This study will be conducted with the highest respect for the individual			
Ethical and Legal Aspects				
	participants in accordance with the requirements of this study protocol			
	and also in accordance with the following:The ethical principles that have their origin in the Declaration of			
	Helsinki.			
	International Conference on Harmonisation E6 Good Clinical			
	Practice: Consolidated Guideline.			
	All applicable laws and regulations, including, without limitation, privacy laws, clinical trial disclosure laws, and regulations.			
	privacy laws, clinical trial disclosure laws, and regulations.			

Table 1. Schedule of study procedures.

	Visit				
	Screening				
The study procedures		Visit 2 Day 1	Visit 3 Day 10	Video visit 4 Day 38	Visit 5 Day 66
Obtaining Informed Consent					
Checking inclusion/exclusion criteria		X			
Collection of anamnesis data					
Conducting a physical examination		X			
Measurement of BMI	X				
Body temperature	X				
Vital signs of the body's condition (mean BP, HR, RR)	X	X	X		X
Randomization		X			
The Rehabilitation Routing Scale (RRS)	X X		X	X	X
The Montreal Cognitive Assessment (MoCA test)			X		X
The Beck Depression Inventory (BDI scale)		X	X	X	X
The Hospital Anxiety and Depression Scale (HADS)		X	X	X	X
The Rivermead index		X	X	X	X
The Muscle Strength Quantitative Rating Scale (MRC)		X	X	X	X
The Post Intensive Care Syndrome (PICS) score		X	X	X	X
The Schulte test		X	X		X
Neurophysiological parameters (EEG, TCDG)		X			
Administration of the study drug intravenously		X	XX		
Dispensation of the study drug for oral administration			X		
Return of the drug and assessment of treatment compliance (if the drug is taken orally)					X
Question about the intake of concomitant drugs		X	X	X	X
Monitoring of adverse events		X	X	X	X

Statistical Analysis Plan

To create conditions for an independent assessment of the obtained results, statistical data processing at the end of the study will be performed by employees not involved in the management of patients participating in the study. Data processing will be performed in the software environment of the TIBCO® StatisticaTM v.13 and R v.4.4.1 and higher packages or similar, corresponding to the tasks of statistical analysis.

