Safety analysis will be performed for the safety population. The following safety parameters are provided for in this study:

- Total number of AEs, stratified by severity and frequency;
- Frequency of AEs, related, in the opinion of the physician-investigator, to the use of the study drug;
- Frequency of serious adverse events (SAEs), related, in the opinion of the physician-investigator, to the use of the study drug;
 - Proportion of patients with at least one AE;
 - Proportion of patients with 2 or more AEs.

The dynamics of quantitative safety parameters relative to baseline values will be assessed and compared with each other using ANOVA with repeated measures. This method allows to simultaneously check for statistically significant dynamics (at least one average value at one time point differs from the others), and also to compare the dynamics and ranges of the indicator values when obtaining the compared drugs. In case of inappropriateness of the use of parametric methods, a similar analysis of the change in the distribution of indicators during therapy will be carried out using non-parametric analogues - the Friedman criterion and the Wilcoxon signed rank criterion, and intergroup comparisons of changes - using the Wilcoxon-Mann-Whitney criterion.

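### The repeated-measures ANOVA planned for quantitative safety parameters would be a complete-case comparison of vital signs, with no sphericity correction stated

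*Combined protocol and SAP*

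**What the plan says.** The safety part of the SAP opens with "Safety analysis will be performed for the safety population"; the document does not define that population. It then lists five adverse-event measures, all counts, frequencies or proportions, for example "Proportion of patients with at least one AE".

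A separate paragraph deals with "The dynamics of quantitative safety parameters relative to baseline values", which are to be "assessed and compared with each other using ANOVA with repeated measures". The alternative applies "In case of inappropriateness of the use of parametric methods": then the SAP turns to "non-parametric analogues - the Friedman criterion and the Wilcoxon signed rank criterion", and to "intergroup comparisons of changes - using the Wilcoxon-Mann-Whitney criterion". The paragraph does not mention missing visits, a sphericity check, an epsilon correction or a covariance structure.

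In Table 1 the quantitative safety measure that is clearly repeated is "Vital signs of the body's condition (mean BP, HR, RR". As extracted, it is marked at screening, Day 1, Day 10 and Day 66, and not at the Day 38 video visit. The table was read by a program, so cells may have shifted.

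**The concern.** Classical repeated-measures ANOVA needs a value from each patient at every analysed visit, and so does the Friedman test. A patient with vital signs on Days 1 and 10 who misses Day 66 therefore contributes nothing to the test, and the observed Day 10 value, taken at the end of the intravenous phase, is lost with the missing one. If leaving is related to a reaction, the comparison loses the patients who carry the signal. The population tested is then narrower than the one named at the start of the same section.

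Separately, the uncorrected F test assumes sphericity. With gaps of 9 and 56 days between Days 1, 10 and 66, serially correlated measurements would violate it and raise the false-positive rate. This second issue concerns the error rate, not who is analysed.

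**Working it through.** The plan gives no dropout rate, correlation or power figure for this analysis, so there is nothing to reproduce. What follows shows scale under stated assumptions.

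**Inputs from the documents:** 60 patients allocated 1:1, taken as 30 per arm; vital signs at Days 1, 10 and 66 plus screening (Table 1); significance level 0.05.

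**1. Patients retained.** Assume a fraction *m* missing independently at each of Days 10 and 66.
- Complete cases = 60 × (1 − *m*)².
- Patients with at least one post-baseline value = 60 × (1 − *m*²).

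| *m* (assumed) | Complete cases | At least one post-baseline value |
|---|---|---|
| 0% | 60 | 60 |
| 2% | 57.6 | 60.0 |
| 5% | about 54 | about 59.9 |
| 10% | 48.6 | 59.4 |
| 15% | about 43 | about 58.7 |

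If values are missing at Day 66 only, 10% missing leaves 60 × 0.9 = 54.

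**2. Possible bias from selection (an extreme illustration).** Assume a true Day 10 shift of 0.5 SD in one arm and none in the other, unit SD, and that every patient above 1.5 SD leaves after Day 10. The mean of those who stay is μ − φ(1.5 − μ)/Φ(1.5 − μ).
- Shifted arm: 0.212, with 15.9% leaving.
- Other arm: −0.139, with 6.7% leaving.
- Completer difference: 0.212 − (−0.139) = 0.351 SD, against a true 0.50 (30% smaller).

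The Day 10 values of those who left exist in this scenario, so an analysis of all available data would use them.

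**3. Error rate of the uncorrected arm-by-visit test.** Assume equal variances and correlation r^(lag in days/10). The lags between Days 1, 10 and 66 are 9, 56 and 65 days. At r = 0.7 the correlations are 0.725, 0.136 and 0.098, so the variances of the pairwise differences, 2(1 − ρ), are 0.55, 1.73 and 1.80. Sphericity requires these to be equal.

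The Greenhouse-Geisser epsilon is [tr A]² / [(k − 1) tr A²], where A is the doubly centred covariance matrix of the k visits. Type I error was simulated with 30 per arm and 200,000 null trials.

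| r per 10 days (assumed) | Epsilon, Days 1/10/66 | Error | Epsilon with screening at Day 0 (assumed) | Error |
|---|---|---|---|---|
| 0.9 | 0.65 | 7.0% | 0.46 | 9.1% |
| 0.7 | 0.74 | 6.4% | 0.54 | 8.3% |
| 0.5 | 0.85 | 5.7% | 0.63 | 7.3% |

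Under compound symmetry epsilon is 1 and the simulated error is 5.0%, whatever the spacing. If the ANOVA were run on changes from baseline at Days 10 and 66 alone, there would be only two repeated levels (k − 1 = 1) and sphericity could not fail. The SAP does not say which visits enter the model.

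**The case against.** The strongest case on the other side is that little of the safety analysis is touched.

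- **Scope.** A reader might infer that the safety analysis as a whole fails to cover the safety population. The documents do not support that. The five listed measures are adverse-event summaries that ANOVA does not touch, so a patient who leaves because of a reaction can still be counted there. The SAP also promises descriptive statistics for safety indicators and their changes by visit and arm, on valid observations. This stands.
- **Which visits matter.** A reader might infer that any missed visit removes a patient. Vital signs are not marked at Day 38, so missing that visit removes nobody from this comparison. The plan also nowhere orders deletion; that follows from the named methods when no other rule is given. Both stand, but the second does not change what the methods would do.
- **Fallback.** The Mann-Whitney test on changes needs only baseline and the visit concerned, and the signed rank test only a pair of visits. Neither is listwise across visits. This stands, but they apply only when parametric methods are judged inappropriate, a trigger that mentions neither missing data nor sphericity. They do not repair the main method.
- **Sphericity.** Uneven spacing does not in itself violate sphericity; it does so in combination with serial correlation, which is plausible but undocumented. This stands, so an inflated error rate cannot be stated as fact.
- **Size.** No missingness rate or correlation is given, and the selection example assumes deterministic dropout that nothing in the plan suggests. This stands.
- **Remedy.** A missing-data rule plus an epsilon correction could be enough. That is a fair alternative, but an epsilon correction alone would leave the Day 10 values of patients who miss Day 66 unused.

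**Conclusion.** The concern holds for one part of the plan: inferential testing of quantitative safety parameters, in practice vital signs. As written, that test is a complete-case analysis, narrower than the named safety population whenever Day 10 or Day 66 values are missing. The loss is zero if no values are missing and about 11 of 60 patients (60 − 48.6) if 10% are missing independently at each of those visits; the true figure is unknown.

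The absent sphericity correction is a second, mild weakness. For Days 1, 10 and 66 under the assumed serial correlation, the error rate is roughly 5.5 to 7% against 5%, and somewhat higher if screening is a further level. It is 5% under compound symmetry.

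This is a minor point about a supportive analysis. It does not bear on the adverse-event results.

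**What to change.** In the SAP's safety paragraph on quantitative parameters, replace the repeated-measures ANOVA with a linear mixed model for repeated measures:

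- terms for arm, visit, arm-by-visit and the baseline value, stating whether baseline is the screening or the Day 1 measurement;
- unstructured covariance, which for two post-baseline visits needs only three parameters and makes no sphericity assumption;
- every available post-baseline value from patients in the safety population, and a definition of that population;
- the between-arm difference with 95% CI at Day 10 and at Day 66.

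The cost is SAP wording; R, which the SAP already names, fits such models. The output is slightly more complex. The model relies on values being missing at random given the observed data. Patients with no post-baseline vital signs still do not contribute, so their number should be reported by arm.

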Study Protocol with Statistical Analysis Plan

Prospective Randomized Study of the modulating effect of MEXIDOL® as an adjuvant stimulant of the cognitive-emotional component of the rehabilitation treatment in patients with acute cerebral failure

NCT Number: NCT06221826

Pharmasoft
April 10, 2023

Study Protocol

The study procedures for the visits are presented in Table 1.

Conditions	Acute Cerebral Failure (Ischemic Stroke, Traumatic Brain Injury)
Study Design	Study Type: Interventional Primary Purpose: Treatment Study Phase: Phase 4 Interventional Study Model: Parallel Assignment Number of Arms: 2 Masking: None (Open Label) Allocation: Randomized (1:1) Enrollment: 60 [Actual] Time Frame: 66 days (I: parenteral therapy 10 days; II: oral therapy 8 weeks)
Arms	Mexidol and Standard Therapy Standard Therapy
Method of Application	Mexidol, solution for intravenous (IV) and intramuscular administration, IV 500 mg for 10 days, then Mexidol FORTE 250, film-coated tablets 250 mg, orally 1 tablet 3 times a day for 8 weeks.
Standard and Concomitant therapy	Standard treatment: basic practices of kinesitherapy, occupational therapy, speech therapy, clinical psychology, supplemented by adjuvant procedures of electrotherapy and rehabilitation environment therapy. The patient's rehabilitation load was at least 3 hours a day for 12 days. Patients may continue their pre-study therapy for other chronic conditions if, in the opinion of the investigator, they do not interfere with the results of this study and are administered at a stable dose during the study.
Primary Purpose	To evaluate the effect of pharmacological modulation of the rehabilitation process with the drug Mexidol as an adjuvant component of rehabilitation treatment of emotional and cognitive disorders in patients with Acute Cerebral Failure (Ischemic Stroke, Traumatic Brain Injury).
Secondary Purpose	To establish the possibility of identifying an individual clinical response to Mexidol therapy (responders and non-responders) and to determine indications for including the drug in an individual rehabilitation program.

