For statistical analysis of quantitative features, compliance with the normal distribution law will be preliminarily assessed by one of the generally accepted methods (Shapiro-Wilk criterion). When testing statistical hypotheses for indicators with a normal distribution, parametric criteria will be used, and for indicators whose distribution differs from normal, nonparametric criteria will be used.

The following indicators will be calculated as descriptive statistics parameters for continuous (quantitative) data:

- n number of valid observations;
- M, Mean arithmetic mean;
- Me, Median median;
- Min minimum value;
- Max maximum value;
- Q1 lower quartile;
- Q3 upper quartile;
- Range range;
- IQR interquartile range;
- SD standard deviation;
- SE standard error of the mean;
- w Wilcoxon-Mann-Whitney test for independent groups;
- t Student's t-test with Welch's correction for independent groups;
- f Fisher's exact test;
- $\gamma 2$ Chi-square test.

For ordinal, categorical and qualitative variables:

- absolute frequency (number of observations);
- relative frequency (expressed as a percentage).

The results of the assessment of quantitative variables, the distribution of which corresponds to the law of normal distribution, will be presented as M±SD, where M is the mean value, and SD is the standard deviation. The results of the assessment of quantitative variables, the distribution of which does not correspond to the law of normal distribution, will be presented as Me [Q1; Q3], where Me is the median, and Q1 and Q3 are the lower and upper quartiles.

Efficacy and safety indicators, as well as their changes, will be presented using descriptive statistics by visits and therapeutic groups. For study visits, qualitative (dichotomous) indicators will be compared between groups based on the Pearson $\chi 2$ criterion, the Pearson $\chi 2$ criterion with Welch's correction, or the Fisher exact test for tables of arbitrary dimension (if the frequency of the indicator in at least one of the subgroups is 5 or less).

Comparison of groups by quantitative indicators can be carried out using the Student's T-test and the Mann-Whitney test. Comparison of intra-group parameters before and after treatment can be

performed using the T-test for related samples or the Wilcoxon-Mann-Whitney test. Statistically significant values are p-level <0.05.

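### The repeated-measures ANOVA for vital signs tests change over time, which says nothing about Mexidol, and its between-arm part is less sensitive than baseline adjustment would be

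*Combined protocol and SAP*

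**What the plan says.** The safety paragraphs that close the Statistical Analysis Plan give the model: "The dynamics of quantitative safety parameters relative to baseline values will be assessed and compared with each other using ANOVA with repeated measures". They name two uses for it. The first is to detect significant dynamics, explained as "at least one average value at one time point differs from the others". The second is "also to compare the dynamics and ranges of the indicator values when obtaining the compared drugs". If parametric methods do not suit, the fallback is Friedman and Wilcoxon signed-rank tests over time, and a Mann-Whitney comparison of changes between groups.

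In Table 1, the vital-signs row ("condition (mean BP, HR, RR") is the only quantitative safety item marked at more than one visit: Screening, Day 1, Day 10 and Day 66. BMI and body temperature are marked once. Randomization and the first infusion are both on Day 1.

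The SAP does not define baseline, list the visits that enter the ANOVA, or say which term (arm main effect or arm-by-visit interaction) carries the arm comparison. It also does not say whether Day 1 vital signs are taken before the infusion.

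**The concern.** The only criterion the SAP spells out for this model is the time test, and that test does not refer to arm. These patients are recovering from acute stroke or brain injury, and both arms receive rehabilitation, so vital signs may well move in both. A significant time test would then be expected whether or not Mexidol does anything.

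The question that matters for safety is whether vital signs differ between arms after treatment starts. For that, the SAP leaves the term open, and power varies widely with the choice. With only 60 patients, a plan that can be carried out in several ways, some of them weak, may miss a real shift in blood pressure, heart rate or respiratory rate. Pre-treatment readings that could sharpen the comparison are already collected.

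**Working it through.** **Inputs from the documents.** Sample size: "Enrollment: 60 [Actual"; allocation: "Allocation: Randomized (1:1"; hence n = 30 per arm, N = 60. Significance level: "Statistically significant values are p-level <0.05". Visits: four, from Table 1.

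**Assumptions.** The documents give no SDs, correlations, effect sizes or power, so there is no planned figure to reproduce. I take SD 1 at each visit, the same correlation ρ between all visits (0.5 to 0.7, with 0.3 as a check), complete data, and Day 1 measured before the infusion. Power comes from the noncentral F distribution with noncentrality λ. Simulations of the same design agreed to within about two percentage points.

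**1. Time test when both arms change equally.** λ = N·Σ(μₜ − μ̄)²/(1 − ρ), df 3 and 174. A 0.3 SD shift at one visit of four gives Σ = 0.09 × 3/4 = 0.0675.
- ρ = 0.5: λ = 60 × 0.0675/0.5 = 8.1; significant in 65% of trials.
- ρ = 0.7: λ = 60 × 0.0675/0.3 = 13.5; 88%.

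The result is the same whether the odd visit is Screening (settling before treatment) or Day 66 (recovery). If the model starts at Day 1, settling drops out and the rate is about 5%. A Day 66 shift is still detected: Σ = 0.09 × 2/3 = 0.06, λ = 7.2 to 12.0, df 2 and 116, 66 to 87%.

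**2. Between-arm terms under the same shared change.** The arm differences are zero at every visit, so λ = 0. The arm effect and the interaction both stay at 5% (simulated 4 to 6%).

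**3. Power for a sustained effect.** Arm difference 0, 0, 0.5, 0.5 SD at the four visits; n/2 = 15.
- Arm-by-visit: λ = 15·Σ(δₜ − δ̄)²/(1 − ρ), with Σ = 4 × 0.25² = 0.25; df 3 and 174.
- Arm main effect: the averaged difference is 0.25, so λ = 15 × 0.25²/[(1 + 3ρ)/4]; df 1 and 58.
- Mean of Days 10 and 66 adjusted for baseline: λ = 15 × 0.5²/v; df 1 and 57. For the two-visit baseline, v = (1 + ρ)/2 − ρ²/[(1 + ρ)/2], which is 0.417 or 0.274 at ρ = 0.5 or 0.7. For one pre-treatment visit, v = (1 + ρ)/2 − ρ², which is 0.50 or 0.36.

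| Test | λ, ρ = 0.5 | λ, ρ = 0.7 | Power |
|---|---|---|---|
| Arm-by-visit, four visits | 7.5 | 12.5 | 61 to 85% |
| Arm main effect, four visits | 1.5 | 1.21 | 23 to 19% |
| Adjusted for Screening/Day 1 mean | 9.0 | 13.7 | 84 to 95% |
| Adjusted for one pre-treatment visit | 7.5 | 10.4 | 77 to 89% |

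At ρ = 0.3 the same rows give 46%, 28%, 76% and 72%.

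**4. Effect at Day 10 only (0.5 SD).**
- Adjusted two-visit mean: λ = 15 × 0.25²/v = 2.25 to 3.43; power 31 to 44%.
- Arm-by-visit: Σ = 0.25 × 3/4 = 0.1875, λ = 5.6 to 9.4; 48 to 72%.
- Adjusted Day 10 value tested at 0.025: residual variance 1 − ρ²/[(1 + ρ)/2] = 0.667 to 0.424, λ = 5.6 to 8.9; 53 to 75%.

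**The case against.** The words about one time point differing are the textbook alternative hypothesis of a time test. A reader might infer that the SAP counts any such difference as a safety signal, or credits shared recovery to Mexidol. It says neither. The 65 to 88% is therefore the chance of detecting a real change over time, not a false-positive rate for the drug. The same sentence, and the fallback, plan an arm comparison, and step 2 shows that it keeps its level. All of this stands.

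A reader might also infer that pre-treatment visits are outcome levels by design and dilute the drug effect. The four-level model is only a reading of Table 1; analysing relative to baseline could equally mean analysing changes. Dilution by averaging affects only an arm main effect, which the SAP does not name. For the interaction, including Screening raises power: 61 to 85% with four visits, against 49 to 72% starting at Day 1.

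The gain also depends on the comparator. If the arms were compared on change from the Screening/Day 1 mean, λ = 15 × 0.25/(1 − ρ) on df 1 and 58 gives 77 to 94%, only 2 to 7 points below the adjusted analysis. Finally, the SAP's list of safety parameters consists of adverse-event counts and proportions, and safety indicators and their changes will be tabulated per visit and arm anyway. That limits the stakes, but it does not settle which test is run.

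**Conclusion.** The point holds in a limited form. The omnibus time test cannot answer the drug question. The between-arm test is valid but, on its most natural reading as arm-by-visit, gives up about 10 to 23 points of power against adjustment for the two-visit baseline (85 against 95% at ρ = 0.7; 61 against 84% at ρ = 0.5). With a single pre-treatment reading the gap is about 4 to 16 points. Because the term is unnamed, an analyst could follow the plan and report a test with power anywhere from about 20% to 85% for the same effect.

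These sizes rest on the assumed 0.5 SD sustained effect, equal correlations of 0.5 to 0.7, no dropout and a pre-infusion Day 1 reading. The documents do not support the stronger conclusion that the plan produces false Mexidol safety signals. This affects how vital signs are interpreted, not the efficacy result.

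**What to change.** In the safety section of the SAP:
- Make the between-arm difference at post-treatment visits the test of a Mexidol effect on vital signs: the mean of Days 10 and 66, and each visit separately, adjusted for the pre-treatment value, with confidence intervals.
- Define baseline as the mean of Screening and Day 1 if Day 1 readings precede the infusion, and as Screening alone otherwise. State which applies.
- Report the pooled change over time as description only.

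The cost is wording; no new data are needed. There are two downsides. The omnibus p-value is no longer a safety result. The two-visit mean is also less sensitive than the interaction to an effect at Day 10 alone (31 to 44% against 48 to 72%), so the per-visit estimates must be kept; tested at 0.025 each, they recover about 53 to 75%. Since enrollment is given as actual and the trial is unmasked ("Masking: None (Open Label"), record whether the change was made before vital-sign data were compared by arm.
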